5.2 SAFETY RECORDING

5.2.1 General assessment of safety

During screening and baseline the patient's condition is assessed. Results of routine observations – demographic data, medical history and concomitant diseases, physical assessment, vital signs, concomitant treatments – will be a part of the check for patient eligibility.

- Medical history/current diseases: Data on previous and current relevant diseases will be collected, in particular information about any cardiovascular disease, hypertension, diabetes mellitus or renal insufficiency.
- Concomitant therapy: Any chronic/concomitant antihypertensive, antiplatelet or anticoagulant treatment or otherwise significant therapy at screening and during the course of the study will be recorded.

- Physical assessment:

It will be done as routine procedure at screening and will be used as check for patient eligibility. It comprises assessment of heart, lung, abdomen, etc. and should be recorded in the source documents. Results will not be collected in the eCRF.

- Vital signs:

Assessment of systolic and diastolic blood pressure and heart rate.

- Haematology:

Haematology laboratory samples (at least haemoglobin, haematocrit, erythrocytes, leucocytes and platelets) will be taken at baseline pre-hospital or, if this is not possible, on hospital arrival, and before hospital discharge according to the local hospital procedures. Values will be recorded in the eCRF as categories relative to the local reference ranges (i.e., below/within/above normal range). In case of bleeding or relevant laboratory abnormalities during the in-hospital period (until discharge) the laboratory values will be cross-checked with baseline values and with adverse events reports.

- Renal function:

Serum creatinine level (as per Cockcroft-Gault formula) should be measured at the first occasion to rule out renal insufficiency. In Group Phi patients with a creatinine clearance of < 30 ml/min, the dose of subsequent enoxaparin injections should be adjusted as described in section 4.1.4.1)²⁷.

- Cardiac markers:

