7.5 DETERMINATION OF SAMPLE SIZE

As mentioned before this is a hypothesis generating trial. No primary hypothesis or primary endpoint have been formulated. Approximately 600 patients are planned to be randomized with 400 receiving PhI therapy and 200 PPCI. A minimum of approximately 100 patients \geq 70 years of age will be randomized to the PhI arm. The aim is to combine ECG and angiographic data from the latter group with similar data from STREAM-1^{16, 18} in order to have a more reliable estimate of the efficacy of the PhI strategy in elderly patients. The analysis of ECG data, angiographic data and clinical events will be described in detail in the statistical analysis plan. Although the study of 600 patients is not powered to show a difference in clinical events, given the elderly nature of the population there will be ample efficacy and safety events to observe. They will be reported along with their 95% confidence limits. For reference, in patients \geq 60 years from STREAM-1 the 30 day composite of death, shock, heart failure and re-MI ranged between 18 and 20 % for PhI and PPCI groups. Bleeding data in this age group were 1.7 % and 0 % ICH and 8.8 % and 7 % non-intracranial major bleeding respectively. If the study would turn into a confirmatory trial after the interim analysis a primary hypothesis on a combined clinical endpoint will be pre-specified.

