## **HISTORY**

Version	Date	Change
1.0	06/09/2022	- Original version
1.1	21/09/2022	

- Limits “additional in-hospital events” to serious in-hospital events (Section 6.6, Table 15.1) to match output of STREAM 1.

- Clarifies in Section 6.6 that PCI (after study PCI) is a planned intervention. It is not recorded if the PCI actually took place.

- Deletes subgroup analyses for safety endpoints

- Deleted multiple imputation sentence and adapted test in Section 9.1.4.1.

1.2	17/11/2022	- Adapted ECG endpoints

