#### **6.6 Additional in-hospital events**

- Serious major arrhythmias (defined as AV block, atrial fibrillation, sustained ventricular tachycardia, ventricular fibrillation or asystole)
- Serious EMD
- Serious cardiac rupture
- Serious acute ventricle septum defect

- Serious pericarditis
- Serious tamponade
- Serious sustained hypotension
- Serious recurrent myocardial ischemia
- Serious abrupt vessel closure
- Serious coronary spasm
- Serious coronary arterial dissection
- Serious hypersensitivity
- Serious anaphylactoid reaction
- Serious thrombocytopenia
- Drop of hemoglobin > 5 g/L
- PCI planned (after study PCI)
- CABG planned (after study catheterization / study PCI)

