### **8.10 Additional in-hospital events**

The number of events and the percentage with respect to the number of subjects for that item will be reported in each treatment group. A Fisher's Exact test will be performed.

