***Table 8.2 Markers of Necrosis (PPS)***

**Table 9.1 Other In-PCI-Hospital Data (FAS)**

	Statistic	Randomised Treatment		P-Value
		Pharmaco-Invasive	Primary PCI	
Patients Enrolled	N	xxx	xxx	
Serum Creatinine [ $\mu\text{mol/L}$ ]	[n] Median (IQR)	[xxx] xxx.x (xxx.x-xxx.x)	xxx] xxx.x (xxx.x-xxx.x)	X.XXX
eGFR [ $\text{mL/min/1.73m}^2$ ]	[n] Median (IQR)	[xxx] xxx.x (xxx.x-xxx.x)	xxx] xxx.x (xxx.x-xxx.x)	X.XXX
Hb A1c				X.XXX
<= 6%	n/N (%)	xx/xxx (xxx.xx%)	xx/xxx (xxx.xx%)	
> 6%	n/N (%)	xx/xxx (xxx.xx%)	xx/xxx (xxx.xx%)	
Haemoglobin [g/dL]				
First available value	[n] Median (IQR)	[xxx] xxx.x (xxx.x-xxx.x)	xxx] xxx.x (xxx.x-xxx.x)	X.XXX
At discharge or Day 4\$	[n] Median (IQR)	[xxx] xxx.x (xxx.x-xxx.x)	xxx] xxx.x (xxx.x-xxx.x)	X.XXX

Randomised Treatment				
	Statistic	Pharmaco-Invasive	Primary PCI	P-Value
Haematocrit [%]				
First available value	[n] Median (IQR)	[xxx] xxx.x (xxx.x-xxx.x)	xxx] xxx.x (xxx.x-xxx.x)	X.XXX
At discharge or Day 4\$	[n] Median (IQR)	[xxx] xxx.x (xxx.x-xxx.x)	xxx] xxx.x (xxx.x-xxx.x)	X.XXX
Thrombocytes				
First available value				X.XXX
Below normal range	n/N (%)	xx/xxx (xxx.xx%)	xx/xxx (xxx.xx%)	
Within normal range	n/N (%)	xx/xxx (xxx.xx%)	xx/xxx (xxx.xx%)	
At discharge or Day 4\$				X.XXX
Below normal range	n/N (%)	xx/xxx (xxx.xx%)	xx/xxx (xxx.xx%)	
Within normal range	n/N (%)	xx/xxx (xxx.xx%)	xx/xxx (xxx.xx%)	
Killip Class at discharge or day 4\$				
Class I	n/N (%)	xx/xxx (xxx.xx%)	xx/xxx (xxx.xx%)	X.XXX

	Randomised Treatment		
	Statistic	Pharmaco-Invasive	Primary PCI
Class II	n/N (%)	xx/xxx (xxx.xx%)	xx/xxx (xxx.xx%)
Class III	n/N (%)	xx/xxx (xxx.xx%)	xx/xxx (xxx.xx%)
Class IV	n/N (%)	xx/xxx (xxx.xx%)	xx/xxx (xxx.xx%)

\$ Whichever comes first.

£: Calculated using the Modification of Diet in Renal Disease (MDRD) formula

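### The haemoglobin-drop event in SAP 6.6 is set at more than 5 g/L (0.5 g/dL), a probable but unproven tenfold unit slip that would flag a large share of patients in a list limited to serious events

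*SAP*

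**What the plan says.** SAP Section 6.6 lists additional in-hospital events, one of which is "Drop of hemoglobin > 5 g/L". Mock Table 15.1 repeats the row with the same number and unit. The SAP history entry for version 1.1 says the list was limited "to serious in-hospital events (Section 6.6, Table 15.1) to match output of STREAM 1". Most rows carry the prefix Serious; the haemoglobin row and the planned PCI and CABG rows do not.

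Section 8.10 gives the analysis: "The number of events and the percentage with respect to the number of subjects for that item will be reported in each treatment group", followed by Fisher's exact test.

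Haemoglobin also appears in mock Table 9.1, where the row label opens "Haemoglobin [g/dL". It is summarised there as a median with interquartile range at two times: "First available value", and discharge or Day 4, whichever is earlier. The same table shows thrombocytes as categories.

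Protocol 5.2.1 describes haematology, haemoglobin included, differently: "Values will be recorded in the eCRF as categories relative to the local reference ranges (i.e., below/within/above normal range".

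The SAP does not say which value the drop is measured from, over what window, or whether the row is computed from laboratory values or reported by the investigator.

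**The concern.** Two features of the SAP point to a unit problem. The same variable appears in g/L in one place and in g/dL in another, a factor of ten apart. And a fall of 0.5 g/dL stands beside cardiac rupture, tamponade and anaphylactoid reaction in a list meant to hold serious events.

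Because 6.6 and Table 15.1 agree, a programmer has no reason to query the figure and will code it as written. The row would then count many patients with small falls. A difference between arms in large falls would be diluted, and a reader could take an unremarkable p-value as information about large drops.

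Separately, the protocol and the SAP disagree on whether haemoglobin is held as a number or as a category, so the data source for the row is unclear.

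**Working it through.** **Unit.** 5 g/L ÷ 10 = 0.5 g/dL. The plan states no expected frequency, power or error rate for this row, so it has no figure of its own to reproduce.

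**Inputs from the documents.** The threshold is above 0.5 g/dL (SAP 6.6, Table 15.1). The planned size is given in protocol 7.5: "Approximately 600 patients are planned to be randomized with 400 receiving PhI therapy and 200 PPCI".

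**Inputs assumed.** The documents give no mean or SD for haemoglobin change. I took the fall as normal, with mean m from 0 to 1.5 g/dL and SD s from 0.6 to 1.5 g/dL.

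**Formula.** Share flagged at threshold c = 1 − Φ((c − m)/s).

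- Lowest share: m = 0, s = 0.6 gives (0.5 − 0)/0.6 = 0.833, share 20.2%.
- Highest share: m = 1.5, s = 0.6 gives (0.5 − 1.5)/0.6 = −1.667, share 95.2%.
- Ten times the threshold, highest share: m = 1.5, s = 1.5 gives (5 − 1.5)/1.5 = 2.333, share 0.98%.

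| Mean fall (g/dL) | Flagged at >0.5 g/dL, SD 0.6 to 1.5 | Flagged at >5 g/dL, largest over the same SDs |
|---|---|---|
| 0 | 20.2% to 36.9% | 0.04% |
| 0.25 | 33.8% to 43.4% | 0.08% |
| 0.5 | 50.0% | 0.14% |
| 0.75 | 56.6% to 66.2% | 0.23% |
| 1.0 | 63.1% to 79.8% | 0.38% |
| 1.5 | 74.8% to 95.2% | 0.98% |

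In 600 patients, 20.2% is about 121 and 95.2% about 571. At ten times the threshold the most is 0.98% × 600, about 6.

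A narrower assumption (mean fall 0.3 to 1.0 g/dL, SD 1.0 to 1.4 g/dL) gives 42% to 69% flagged, and at most about 0.2% at ten times the threshold.

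**Effect on the Fisher test (illustration).** Suppose true large drops occur in 8% of 400 PhI patients and 2% of 200 PPCI patients. Both rates are assumed. Let a fraction b of the remaining patients be flagged for small falls. The flagged rates are 0.08 + 0.92b and 0.02 + 0.98b, so the difference shrinks to 0.06 × (1 − b). Exact power of the two-sided 5% test:

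| b | Flagged, PhI vs PPCI | Difference | Power |
|---|---|---|---|
| 0 | 8.0% vs 2.0% | 6.0 points | 89% |
| 0.2 | 26.4% vs 21.6% | 4.8 points | 24% |
| 0.5 | 54.0% vs 51.0% | 3.0 points | 10% |
| 0.8 | 81.6% vs 80.4% | 1.2 points | 6% |

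**Recording of haemoglobin.** Protocol 5.2.1 stores haematology as below, within or above the local range. SAP Table 9.1 plans numeric haemoglobin at two times. Both cannot describe the same eCRF field. A drop in g/L needs the numeric version, unless the investigator reports the event directly.

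**The case against.** The strongest reply is that g/L is a valid unit, the two SAP entries agree with each other, and the value may be deliberate. Proof of a slip would need the eCRF or the STREAM-1 output, and neither is available. That stands: the documents support a check, not a declared error.

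Four stronger readings are tempting, and the documents do not carry them.

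- A reader might infer that about half of all patients would be flagged. That holds only if the mean fall is near 0.5 g/dL, and no document gives a mean. The defensible statement is about one fifth or more under the stated assumptions.
- A reader might infer from protocol 5.2.1 that the event cannot be derived. Table 9.1 plans numeric haemoglobin at two times, from which a drop could be calculated, and it treats platelets, by contrast, as categorical. The row may also be investigator-reported. What remains is a contradiction between the two documents.
- A reader might treat the row as the trial's bleeding signal. The SAP gives it no such role. Bleeding is assessed in SAP 6.3, with definitions in protocol Appendix B based on transfusion and haemodynamic compromise; those endpoints do not use this threshold.
- A reader might say the SAP labels a 0.5 g/dL fall as serious. The history entry limits the list, but the row itself has no such prefix.

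A normal model is also weak in the far tail, where bleeding drives the largest falls. The 0% to 1% figure therefore shows the tenfold gap and does not forecast serious falls. The share above 0.5 g/dL lies nearer the centre of the distribution and depends less on the tail.

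**Conclusion.** The point holds as a probable tenfold unit slip to be verified. The firm parts are these: 5 g/L equals 0.5 g/dL, the unit differs from Table 9.1, the figure sits in a list restricted to serious events, and the protocol and SAP disagree on how haemoglobin is recorded.

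The size rests on assumed means and SDs: about 20% to 95% flagged as written, against 0% to 1% at ten times the value. Across that range the between-arm test on this row is nearly uninformative about large drops. The power figures depend further on the assumed 8% and 2%.

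The consequence is small. The trial is exploratory, and the row is descriptive, outside the primary-interest, secondary and combined endpoints, and not imputed, pooled or used in subgroups. It is still worth correcting, because a stated threshold determines a reported result.

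**What to change.** 1. Check the threshold and unit against the eCRF and the STREAM-1 output that the list is meant to match. The documents do not show which value was intended, so none should be substituted without that check.
2. Correct SAP 6.6 and Table 15.1 together, in the unit used in Table 9.1.
3. State whether the row is laboratory-derived or investigator-reported. If derived, give the reference value and window, for example from the first available value to discharge or Day 4.
4. Reconcile protocol 5.2.1 with Table 9.1 on whether haemoglobin is recorded numerically.
5. Remove the row only if numeric values were not collected and the event is not investigator-reported.

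The cost is a few lines of SAP text, one derivation, and a clarification of protocol 5.2.1 if the eCRF holds numeric values. No sample size or other endpoint analysis changes.

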## 7 Interim analysis

At the interim analysis when about 300 patients were randomized, it was decided the study would continue as planned and the study remains of exploratory nature based on descriptive p-values with estimation of 95% confidence limits for formal statistical hypotheses generation.

## 8 Statistical Methods

Statistical analysis will be programmed using the SAS® system version 9.4 or higher.

### 8.1 Multiple imputation analyses

In case multiple imputations are performed to deal with missing data, the results will be combined over the different imputations following Li, Raghunathan and Rubin (1991) as implemented in PROC MIANALYZE.

### 8.2 Baseline Characteristics

For the continuous variables, the mean, standard deviation (SD), median, and range will be reported in each treatment group and a t-test or Wilcoxon-test will be used, whichever is appropriate. For the discrete variables, the number of

subjects in each category and the percentage with respect to the number of subjects with non-missing information for that item will be reported in each treatment group. A chi-square test for an r x 2 contingency table will be performed for all categorical variables.

P-values for baseline characteristics will be calculated only for descriptive purposes.

The estimated Glomerular Filtration Rate (eGFR) will be calculated with the Modification of Diet in Renal Disease (MDRD) formula (Levy et al. (2006). That is,

$$\text{eGFR} = 175 \times (\text{Serum Creatinine in mg/dL})^{-1.154} \times (\text{age})^{-0.203} \times 0.742 \text{ (if female)} \\ \times 1.212 \text{ (if black)}.$$

### **8.3 Treatment compliance**

Treatment compliance will be described using descriptive statistics.

### **8.4 Concomitant Medications**

The number of subjects in each study group who have taken concomitant medications during hospitalization as recorded in the CRF will be reported. The percentage of subjects will be calculated with respect to the number of subjects with non-missing information for that particular item. A Fisher's Exact test will be used to assess potential treatment differences, p-values will be presented.

### **8.5 Efficacy endpoints of primary interest**

#### **8.5.1 Clinical endpoint**

The primary efficacy endpoint will be analysed by presenting the event rates and the 95% confidence intervals (two-sided) separately for each treatment group. In addition, the two treatment groups will be compared using a working Poisson regression model (Zhou (2004)) from which the between-group comparison will be estimated by means of a relative risk with a 95% confidence interval (two-sided).

In case there are no events in a particular treatment group (before imputation), an artificial observation in each cell (treatment group by event) with weight 0.5 will be added in order to estimate the relative risk.

Furthermore, the risk difference with a 95% confidence interval will be calculated using PROC FREQ.

Standard multiple imputation methodology as described in Section 8.1 will be applied to combine the results over the different multiple imputations, if applicable.

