## **Pooled Elderly Set – Intention to treat (PES-I)**

The combined sets of the following subjects:

- Patients  $\geq 75$  years from STREAM 2
- Patients  $\geq 75$  years from STREAM 1 who are randomized after protocol amendment 2.

Subjects will be analysed according to the treatment group to which they were randomized.

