## **Pooled Elderly Set – Per protocol (PES-P)**

The combined sets of the following subjects:

- Patients  $\geq 75$  years from STREAM 2 who belong to the PPS
- Patients  $\geq 75$  years from STREAM 1 who belong to the PPS and are randomized after protocol amendment 2.

Subjects will be analysed according to the treatment group to which they were randomized

Given that no per protocol set was defined in STREAM I, during the blinded review meeting also the relevant patients of STREAM I will be reviewed blinded to outcome in order to include them in the PES-P set. All major protocol deviations that lead to exclusion from the PES-P will be fully documented in Analysis Sets Specification Document that will be dated and signed prior to database lock.

The primary efficacy and safety analyses will be based on FAS. The PPS will serve for sensitivity analyses. The PES-I and PES-P will be used to have a more reliable estimate of the efficacy and safety of the PhI strategy in elderly patients for a selection of endpoints (see Section 9).

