### 9.1 Efficacy endpoints of primary interest

#### 9.1.1 Clinical endpoint

The results from STREAM 1 and 2 will be combined using the Mantel-Haenszel method. Assume that  $\hat{r}_h$  and  $\hat{V}_h$  are the point estimates of  $r_h = (\pi_{hA} \pi_{hB})$ , with  $\pi_{hA}$  and  $\pi_{hB}$  the event rates in both treatment groups, and its variance-covariance matrix in study h, where  $h = 1, 2$ . Define  $w_h = \frac{n_{hA}n_{hB}/n_h}{\sum_{h=1}^2 (n_{hA}n_{hB}/n_h)}$ ,  $h=1, 2$ , and then  $\hat{r} = \sum_{h=1}^2 w_h \hat{r}_h$  and  $V = \sum w_h^2 V_h$  with  $n_{hA}$  and  $n_{hB}$  the sample size in group A and B in study h, respectively, and  $n_h$  the total sample size in study h.

Assume that  $\hat{r} = \begin{pmatrix} \hat{r}_A \\ \hat{r}_B \end{pmatrix}$  and the relative risk can be estimated by  $\varphi = \frac{\hat{r}_A}{\hat{r}_B}$ .

The confidence intervals and the overall test are calculated after logarithmically transforming the relative risks ( $=\log(\varphi)$ ).

Denote by  $\hat{r}_t = (\log(\hat{r}_A) \quad \log(\hat{r}_B))'$  and  $V_t$  respectively the logarithmically transformed rates and the corresponding variance-covariance matrix.

Let  $s = (1 \quad -1)$  then  $Q = (s\hat{r}_t)'(sV_t s')^{-1}(s\hat{r}_t)$  is a test statistic which has approximately a chi-square distribution with 1 degree of freedom under the hypothesis  $H_0: \phi = 1$  (vs  $H_a$ : otherwise).

Let  $s = (1, -1)$ , the 95% confidence interval for the relative risk of treatment A versus B will be calculated by  $\exp(s\hat{r}_t \pm 1.96\sqrt{sV_t s'})$ .

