## **9.2 Safety Secondary Endpoints**

Total fatal stroke, total disabling stroke, total non-disabling stroke, intracranial haemorrhage, ischaemic stroke, total stroke (all types), major non-intracranial bleeds including blood transfusions, minor non-intracranial bleeds and total non-intracranial bleeds will be analysed similarly as Section 9.1.1.

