**Table 25.2 Angiographic endpoints (PES-P)**

**Table 26.1 Safety secondary endpoints at day 30 (PES-I)**

	PhI (N=#)	P-PCI (N=#)	Relative Risk	P-value	PhI Better	P-PCI Better
Total fatal stroke	n/N (%)	n/N (%)	#	#		
Total disabling stroke	n/N (%)	n/N (%)	#	#		
Total non-disabling stroke	n/N (%)	n/N (%)	#	#		
Intracranial haemorrhage	n/N (%)	n/N (%)	#	#		
Ischaemic stroke	n/N (%)	n/N (%)	#	#		
Total stroke (all types)	n/N (%)	n/N (%)	#	#		
Major non-intracranial bleeds including blood transfusions	n/N (%)	n/N (%)	#	#		
Minor non-intracranial bleeds	n/N (%)	n/N (%)	#	#		
Total non-intracranial bleeds	n/N (%)	n/N (%)	#	#		

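### The pooled elderly ICH analysis (SAP 9.1.1, 9.2) has no rule for an arm without events, and the rule in SAP 8.5.1 prints a relative risk of 0.50 when neither arm has an event

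*SAP*

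**What the plan says.** **Full analysis set.** SAP 8.5.1 plans event rates with 95% intervals per arm, a relative risk from a working Poisson model, and a risk difference from PROC FREQ whose interval type is not named. If an arm has no events before imputation, "an artificial observation in each cell (treatment group by event) with weight 0.5 will be added in order to estimate the relative risk". SAP 8.7 sends the safety endpoints, including ICH, to this section.

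**Pooled elderly sets.** SAP 4 combines STREAM-2 patients aged 75 or over with STREAM-1 patients of that age "who are randomized after protocol amendment 2". These sets "will be used to have a more reliable estimate of the efficacy and safety of the PhI strategy in elderly patients". SAP 9.1.1 weights the study rates by Mantel-Haenszel weights and estimates the relative risk as r_A/r_B. It then states: "The confidence intervals and the overall test are calculated after logarithmically transforming the relative risks". The two inputs, r_t and V_t, are "respectively the logarithmically transformed rates and the corresponding variance-covariance matrix". SAP 9.2 lists the stroke endpoints, ICH and the bleeds, and ends: "total non-intracranial bleeds will be analysed similarly as Section 9.1.1". Neither 9.1.1 nor 9.2 says what happens when a rate is zero, refers to 8.5.1, or plans a risk difference.

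**Background rates.** Protocol 7.5 gives STREAM-1 ICH at age 60 or over as 1.7% with PhI and 0% with PPCI. Protocol 1.1 reports no further ICH in 97 PhI patients aged 75 or over after the dose was halved.

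**The concern.** The SAP foresees empty arms in the full analysis set, but not in the smaller pooled set, where they are more likely. The log of a zero rate does not exist, so the planned pooled ICH test and interval may not be computable. Someone would then have to choose a method after seeing which arm is empty, and that choice would be data-driven.

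The rule that does exist adds the same half-observation to arms of different size. With no ICH in either arm, it reports a relative risk well below 1 that reflects only the allocation ratio.

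Comparing ICH incidence is part of main objective 2 in protocol 1.1, and the pooled sets exist to firm up the safety estimate in the elderly.

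**Working it through.** The documents state no probability of an empty arm and no corrected relative risk, so there is no figure to reproduce.

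**Inputs.** 400 PhI and 200 PPCI (protocol 7.5); the STREAM-1 ICH figures above; the 0.5 rule (SAP 8.5.1).

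**Assumptions.** STREAM-1 amendment 2 is the dose change described in protocol 1.1. The 0% with PPCI means no events. The number of STREAM-2 patients aged 75 or over is not given (only about 100 PhI patients aged 70 or over), so I use 40/20, 80/40 and 120/60.

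**1. What 9.1.1 returns.** With both STREAM-1 rates zero, each pooled rate is w_2 times the STREAM-2 rate at age 75 or over.
- PPCI empty (with or without PhI events): r_A/r_B is undefined.
- Only PhI empty: the relative risk is 0, with no test or interval.
- A test and interval exist only with at least one STREAM-2 ICH in each arm.

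**2. How often.** For a common rate p, let A = (1−p)^n_PhI and B = (1−p)^n_PPCI. Test and interval are undefined with probability A + B − AB. The relative risk is undefined with probability B, and is 0 with probability A(1−B).

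| PhI/PPCI aged ≥75 | p | Test and CI undefined | RR undefined | RR = 0, no CI |
|---|---|---|---|---|
| 40/20 | 0.5% | 98% | 90% | 8% |
| 40/20 | 1% | 94% | 82% | 12% |
| 80/40 | 0.5% | 94% | 82% | 12% |
| 80/40 | 1% | 82% | 67% | 15% |
| 120/60 | 0.5% | 88% | 74% | 14% |
| 120/60 | 1% | 68% | 55% | 14% |

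For example, at 80/40 and 1%: A = 0.99^80 = 0.448, B = 0.99^40 = 0.669, and A + B − AB = 0.817. If the true PPCI rate is 0, then B = 1 and the result is always undefined.

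**3. If the 0.5 rule were fed into 9.1.1.** Take STREAM-1 as 0/97 v 0/97 (the PPCI size is assumed) and STREAM-2 as 100 v 50 (assumed). No STREAM-2 events gives a pooled RR of 0.72 (0.04 to 11.9); 2 v 0 gives 1.87 (0.19 to 18.2). With no events anywhere, the STREAM-1 stratum is neutral at equal sizes. The departure from 1 therefore comes from the 2:1 STREAM-2 stratum, where (0.5/101)/(0.5/51) = 0.50.

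**4. Full analysis set, 400 v 200.** The fixed rule is RR = [(a+0.5)/401]/[(b+0.5)/201]. For comparison, a correction proportional to arm size adds 2/3 to each PhI cell and 1/3 to each PPCI cell.

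| ICH, PhI v PPCI | Fixed 0.5 | Proportional |
|---|---|---|
| 0 v 0 | 0.50 | 1.00 |
| 1 v 0 | 1.50 | 2.50 |
| 7 v 0 | 7.5 | 11.5 |
| 0 v 1 | 0.17 | 0.25 |

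Seven v 0 is about what the STREAM-1 rates imply (400 × 0.017 = 6.8). At least one arm is empty with probability 75%, 45% and 15% at equal rates of 0.25%, 0.5% and 1%. Both are empty with probability 22%, 5% and 0.2%, and with probability 0.983^400 = 0.1% at the STREAM-1 rates.

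**5. Risk-difference interval at 4 v 0.** Wald: 0.01 ± 1.96 × √(0.01 × 0.99/400), or 0.02% to 1.98%, which excludes 0. Newcombe: −0.98% to 2.54%. Miettinen-Nurminen: −0.89% to 2.54%. Fisher p = 0.31.

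**The case against.** The strongest reply is that 9.1.1 takes the study-level estimates as given and does not say how they are obtained. If the 8.5.1 rule supplies them, the pooled result exists and one clarifying line is enough. That reading is possible, but the SAP does not state it, and it would carry the allocation artefact of step 3 into the pooled relative risk.

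Much is also already covered. The full analysis set has per-arm intervals and a risk difference, and Table 26.1 shows pooled counts per arm. The trial is exploratory, and no method can make so few ICH events informative. All this stands and limits the harm. The pooled section still has no between-arm measure to fall back on.

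A reader might infer three stronger points that do not hold:
- **That the fixed 0.5 biases ICH in favour of PhI.** The shift is relative to a proportional correction, which is not uniformly closer to the truth. Geometric mean RRs, with the correction applied only when an arm is empty, are 0.90 (fixed) v 1.12 (proportional) at equal rates of 0.5%, and 3.33 v 3.90 at 1.7% v 0.5% (true 3.4). The proportional rule is nearer at lower rates (equal 0.25%: 0.74 v 1.10). At 5 v 0 its interval already excludes 1 (1.02 to 70.7) although Fisher p = 0.18.
- **That the variance handling is open.** SAP 8.5.1 plainly describes a weighted record; nothing there suggests a frequency weight.
- **That pooled bleeds are affected too.** STREAM-1 major non-intracranial bleeding was 8.8% and 7%, so an empty pooled arm is implausible for the common bleeds.

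**Conclusion.** The gap in 9.1.1/9.2 is real. As written, the pooled ICH comparison would lack a test and interval in 68% to 98% of trials over the assumed sizes and rates, and always if the PPCI rate is 0. This rests on the reading of amendment 2, on 0% meaning no events, and on the assumed numbers aged 75 or over. The other stroke endpoints go through the same formula, but the documents give no rates for them, so only ICH is quantified.

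In the full analysis set, the RR of 0.50 at 0 v 0 comes from allocation alone. With one empty arm, the relative risk depends strongly on the correction chosen, and neither correction considered is uniformly better. The documents do not support calling the 0.5 rule a general bias towards PhI.

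This should be fixed, but its reach is limited. Protocol Appendix B asks for consistency across endpoints and later confirmation before a difference counts, and the composite of primary interest, at 18% to 20% in STREAM-1, is unaffected.

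**What to change.** - **SAP 9.1.1/9.2:** when a pooled arm has no events, replace the log relative-risk test and interval by a study-stratified Mantel-Haenszel risk difference. Keep the 9.1.1 weights and name an interval that is defined with empty cells (stratified Newcombe or score). Example: 0/97 v 0/97 plus 1/80 v 0/40 (all sizes assumed except the PhI 97) has weights 0.645 and 0.355. It gives 0.355 × 1/80 = 0.44%, with a stratified Newcombe interval of −3.5% to 3.6%.
- **SAP 8.5.1/8.7, both arms empty:** report the relative risk as not estimable.
- **SAP 8.5.1/8.7, one arm empty:** make the planned per-arm intervals exact. The upper limit is 1 − 0.025^(1/n): 0.92% for 0/400 and 1.83% for 0/200. Add Fisher's exact p, already used in 8.4 and 8.10, and label any corrected relative risk as correction-dependent.
- **SAP 8.5.1, risk difference:** name a non-Wald interval in advance, Newcombe or Miettinen-Nurminen. Newcombe is the more cautious: at 8 v 0 it gives −0.13% to 3.90%, against 0.10% to 3.90%.

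The cost is SAP wording and a few SAS options, with no new data. Intervals will be wider than Wald, and some rows will show a risk difference in place of a relative risk.
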